10.3.2. Definition of SAE

If an event is not an AE per definition above, then it cannot be an SAE even if serious conditions are met (e.g., hospitalisation for signs/symptoms of the disease under study, death due to progression of disease).

An SAE is defined as any serious adverse event that, at any dose:

- a. Results in death
- b. Is life-threatening

The term ‘life-threatening’ in the definition of ‘serious’ refers to an event in which the participant was at risk of death at the time of the event. It does not refer to an event, which hypothetically might have caused death, if it were more severe.

c. Requires inpatient hospitalisation or prolongation of existing hospitalisation
 
 • In general, hospitalisation signifies that the participant has been admitted (usually involving at least an overnight stay) at the hospital or emergency ward for observation and/or treatment that would not have been appropriate in the physician’s office or outpatient setting. Complications that occur during hospitalisation are AE. If a complication prolongs hospitalisation or fulfils any other serious criteria, the event is serious. When in doubt as to whether “hospitalisation” occurred or was necessary, the AE should be considered serious. • Hospitalisation for elective treatment of a pre-existing condition that did not worsen from baseline is not considered an AE.

d. Results in persistent or significant disability/incapacity
 
The term disability means a substantial disruption of a person’s ability to conduct normal life functions.
 
This definition is not intended to include experiences of relatively minor medical significance such as uncomplicated headache, nausea, vomiting, diarrhoea, influenza, and accidental trauma (e.g., sprained ankle) which may interfere with or prevent everyday life functions but do not constitute a substantial disruption.

e. Is a congenital anomaly/birth defect


f. Other situations:
 
 • Medical or scientific judgment should be exercised by the investigator in deciding whether SAE reporting is appropriate in other situations such as significant medical events that may jeopardise the participant or may require medical or surgical intervention to prevent one of the other outcomes listed in the above definition. These events should usually be considered serious. 
 ○ Examples of such events include invasive or malignant cancers, intensive treatment for allergic bronchospasm, blood dyscrasias, convulsions, or development of intervention dependency or intervention abuse.

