2.3.1. Risk Assessment

Risks are summarised in the table below. Additional withdrawal/stopping criteria for liver chemistry, drug induced vascular inflammation (DIVI), haematology, renal function, and PK are discussed in Section 7.1.

Potential Risk of Clinical Significance	Summary of Data/Rationale for Risk	Mitigation Strategy
Investigational Product (IP) [GSK3228836]		

Nonclinical Risks: Drug Induced Vascular Inflammation and Complement Activation
	
Inflammatory and immune changes are recognised as a class effect of antisense oligonucleotides (ASOs). Vasculitis and/or perivascular inflammation has been described in monkey studies with many if not most ASOs.
 
This effect has not been observed in clinical studies with GSK3228836 to date.
	
Laboratory Evaluations: Inclusion of biomarker panels to look for inflammatory and immune activation that would be expected to accompany vascular inflammation
 
Stopping Criteria: Proposed Monitoring Schedule and Stopping Rules for Drug Induced Vascular Inflammation and Complement Activation (see Section 7.1.4)

Clinical Risks: Drug induced liver injury / ALT Flares
	
The liver is a site of accumulation of antisense oligonucleotides. Liver findings in nonclinical studies of GSK3228836 were generally limited to mild hepatic enzyme elevations associated with hepatic vacuolation without concomitant histologic evidence of degeneration in mice, consistent with findings noted with other 2'-methoxyethyl (MOE) ASOs. Review of the available clinical data indicates liver enzymes are increased on treatment with ASOs in a low percentage of patients compared to placebo.
 
Alanine aminotransferase (ALT) elevations (defined as ALT ≥2X upper limit normal (ULN)) were observed in the ISIS 505358-CS3 study. Reductions in HBsAg were temporally associated with ALT elevation in all 11 participants with ALT elevations. HBsAg reduction either preceded the ALT elevations or took place concomitantly with ALT flares. There were no changes in bilirubin.
	
Laboratory Evaluations: hepatic enzyme monitoring as presented in Table 9
 
Stopping Criteria: ALT flares are expected in the study population. Monitoring and stopping criteria are presented in Section 7.1.1

Potential Risk of Clinical Significance	Summary of Data/Rationale for Risk	Mitigation Strategy

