8.3.7. GSK3228836-Related Adverse Events of Special Interest

8.3.7.1. ALT Increases

The liver is a site of accumulation of antisense oligonucleotides and this has been exploited in the treatment of liver related diseases.

Outside the setting of disease reactivation or rebound viremia, the etiology of ALT increase (flares) in CHB patients is currently uncertain. It has been postulated that ALT flares are evidence of reactivation of the immune system in the liver with accompanying clearance of infected hepatocytes, particularly when observed during immunotherapy or spontaneous loss of HBsAg. Therapeutic ALT flares have been shown to correlate with antiviral effect in blood (i.e. declines in HBV DNA, and/or HBsAg).

A monitoring strategy of ALT is presented in Section [7.1.1](#)

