1. Platelets will require local/central lab collection while participants are GSK3228836 on-treatment. The blood draw can be taken the day before GSK3228836 dosing. Results must be available prior to dosing.
2. Urine testing will be standard for the protocol unless serum testing is required by local regulation or IRB/IEC or if urine testing is unavailable
3. Details of liver chemistry stopping criteria and required actions and follow-up assessments after liver stopping or monitoring event are given in Section 7.1 and Appendix 6. All events of ALT $\geq 3 \times$ upper limit of normal (ULN) and bilirubin $>2 \times$ ULN ($>35\%$ direct bilirubin) or ALT $\geq 3 \times$ ULN and international normalised ratio (INR) >1.5 , if INR measured, which may indicate severe liver injury (possible Hy's Law), must be reported as an SAE (excluding studies of hepatic impairment or cirrhosis).

10.3. Appendix 3: AEs and SAEs: Definitions and Procedures for Recording, Evaluating, Follow-up, and Reporting

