10.3.1. Definition of AE

AE Definition

 An AE is any untoward medical occurrence in a clinical study participant, temporally associated with the use of a study intervention, whether or not considered related to the study intervention. 
NOTE: An AE can therefore be any unfavourable and unintended sign (including an abnormal laboratory finding), symptom, or disease (new or exacerbated) temporally associated with the use of a study intervention.

Definition of Unsolicited and Solicited AE

 An unsolicited adverse event is an adverse event that was not solicited using a Participant Diary and that is communicated by a participant/ legally acceptable representative (LAR(s)) who has signed the informed consent. Unsolicited AEs include serious and non-serious AEs. Potential unsolicited AEs may be medically attended (i.e., symptoms or illnesses requiring a hospitalisation, or emergency room visit, or visit to/by a health care provider). The participants/LAR(s) will be instructed to contact the site as soon as possible to report medically attended event(s), as well as any events that, though not medically attended, are of participant /LAR's concern. Detailed information about reported unsolicited AEs will be collected by qualified site personnel and documented in the participant's records. Unsolicited AEs that are not medically attended nor perceived as a concern by participant/LAR(s) will be collected during interview with the participants/ LAR(s) and by review of available medical records at the next visit. Solicited AEs are predefined local at the injection site and systemic events for which the participant is specifically questioned, and which are noted by the participant in their diary.

Events Meeting the AE Definition

 Any abnormal laboratory test results (haematology, clinical chemistry, or urinalysis) or other safety assessments (e.g., ECG, radiological scans, vital signs measurements), including those that worsen from baseline, considered clinically significant in the medical and scientific judgment of the investigator (i.e., not related to progression or part of underlying disease).

- Exacerbation of a chronic or intermittent pre-existing condition including either an increase in frequency and/or intensity of the condition.

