- New conditions detected or diagnosed after study intervention administration even though it may have been present before the start of the study.
- Signs, symptoms, or the clinical sequelae of a suspected intervention- intervention interaction.
- Signs, symptoms, or the clinical sequelae of a suspected overdose of either study intervention or a concomitant medication. Overdose per se will not be reported as an AE/SAE unless it is an intentional overdose taken with possible suicidal/self-harming intent. Such overdoses should be reported regardless of sequelae.
- “Lack of efficacy” or “failure of expected pharmacological action” per se will not be reported as an AE or SAE. Such instances will be captured in the efficacy assessments. However, the signs, symptoms, and/or clinical sequelae resulting from lack of efficacy will be reported as AE or SAE if they fulfil the definition of an AE or SAE.

Events NOT Meeting the AE Definition

- Any clinically significant abnormal laboratory findings or other abnormal safety assessments which are associated with the underlying disease, unless judged by the investigator to be more severe than expected for the participant’s condition.
- The disease/disorder being studied or expected progression, signs, or symptoms of the disease/disorder being studied, unless more severe than expected for the participant’s condition.
- Medical or surgical procedure (e.g., endoscopy, appendectomy): the condition that leads to the procedure is the AE.
- Situations in which an untoward medical occurrence did not occur (social and/or convenience admission to a hospital).
- Anticipated day-to-day fluctuations of pre-existing disease(s) or condition(s) present or detected at the start of the study that do not worsen.

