4.5.2.1. Adverse Events of Special Interest

The following AEs of special interest will be reported:

- ALT increase
- Vascular inflammation and complement activation
- Thrombocytopenia
- Renal injury

An up-to-date list of specific MedDRA Queries (SMQs), high level terms (HLTs) or individual preferred terms (PTs) used to identify adverse events of special interest (AESIs) is periodically updated and stored in a central location. At the time of database lock, the latest version of the terms will be extracted and used to identify AESIs.

All AEs of special interest will be summarized by SOC and PT, and, also summarized by SOC, PT and maximum grade. Serious AESIs will be summarized by SOC and PT. All AEs of special interest will be listed.

Separate outputs will be created for each AESI category (ALT increase, vascular inflammation and complement activation, thrombocytopenia, renal injury) to explore the data in more detail if data permits.

Event Characteristics: The characteristics of all event occurrences during the post-baseline period will be summarized, which looks at event characteristics (serious, drug-related, leading to withdrawal, severe or Grade 3-4, fatal), number of events per participant, outcome, maximum grade or intensity and action taken.

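### The AE and SAE definitions conflict with the ALT AESI and the possible Hy's Law SAE rule, so recording a hepatitis flare depends on investigator judgement

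*Protocol*

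**What the plan says.** **Text that keeps a flare out of the AE and SAE records**

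- Protocol Section 10.3.1 lists, among events that are not AEs, abnormal laboratory findings "which are associated with the underlying disease, unless judged by the investigator to be more severe than expected". A second bullet treats expected signs and symptoms of the disease under study in the same way, with the same severity exception. Section 8.2.5 repeats the laboratory carve-out where it defines clinically significant results.
- Section 10.3.2 states: "If an event is not an AE per definition above, then it cannot be an SAE even if serious conditions are met". Its examples are hospital admission for signs of the studied disease and death from its progression.
- Section 2.3.1 says, for both drugs, that "ALT flares are expected in the study population". Section 4.2 records the sponsor's belief that flares are therapeutic and reflect immune clearance of the virus.

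**Text that brings a flare in**

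- Section 10.3.1 also lists as an AE "Exacerbation of a chronic or intermittent pre-existing condition including either an increase in frequency and/or intensity of the condition".
- Section 8.3.7.1 places ALT increase among the GSK3228836 AESIs. SAP Section 4.5.2.1 opens its list, with ALT increase first, by saying "The following AEs of special interest will be reported". It identifies AESIs from MedDRA queries and terms.
- Table 17 note 3 (Section 10.2) covers all events with ALT at least 3 x ULN plus bilirubin above 2 x ULN (more than 35% direct), or plus INR above 1.5. These "must be reported as an SAE (excluding studies of hepatic impairment or cirrhosis"). That exclusion does not release this trial, because Section 5.2 excludes participants with cirrhosis.

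**The concern.** Chronic hepatitis B is the disease under study, and a hepatitis flare is a main hepatic risk of both drugs. A carve-out for the underlying disease therefore lands on the hepatic safety signal itself. Section 8.3.7.1 adds to the ambiguity: "It has been postulated that ALT flares are evidence of reactivation of the immune system in the liver". An investigator who accepts that view may treat a flare as hepatitis B responding to treatment rather than as an adverse event.

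The stake is the safety record. An ALT rise with no AE entry cannot reach the coded ALT AESI table, the related-AE table or the SAE table. It also does not start the 24-hour report that Section 8.3.1 requires for SAEs. The investigator knows the arm and the treatment phase when making this judgement.

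**Working it through.** No sample size, power or event figure is involved, so the check is to apply the texts to the same event and then see what other records would hold.

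**Case 1: ALT above 10 x ULN on PegIFN, bilirubin normal, participant admitted to hospital.**

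- *Reading A.* The flare is attributed to hepatitis B and was foretold in Section 2.3.1. Under the Section 10.3.1 exclusions it is not an AE. Under Section 10.3.2 it then cannot be an SAE, and admission for the studied disease is one of that section's own examples.
- *Reading B.* The flare is an exacerbation of a chronic pre-existing condition, so it is an AE under Section 10.3.1. Admission meets a seriousness criterion, so it is an SAE due within 24 hours. It is also an ALT AESI.

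Both readings follow current text, and no sentence ranks them.

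**Case 2: ALT at least 3 x ULN with bilirubin above 2 x ULN, more than 35% direct.** Table 17 note 3 makes this an SAE without qualification. Section 10.3.2 makes SAE status conditional on AE status and has no exception for note 3. The duty exists, but it stands in a footnote to a laboratory table and the general definition contradicts it.

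**Does Section 8.3.7 settle it?** For injection site reactions, Section 8.3.7.5 says outright that they should be reported as AEs. Section 8.3.7.1 contains no such instruction for ALT increases and only points to the monitoring strategy in Section 7.1.1.

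**What remains if no AE is recorded?**

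| Route | Covers | Does not cover |
|---|---|---|
| Liver Event CRF (Section 7.1.1, Appendix 6) | GSK3228836 liver stopping criteria, with Medical Monitor notice in 24 hours | PegIFN ALT elevations: Section 7.2.2 asks for no such form |
| Hepatitis symptoms on the AE CRF (Section 7.1.1) | New or worsening symptoms, as relevant | ALT rises without symptoms |
| Death CRF (Section 8.3.6) | Every death, SAE or not | Non-fatal events; it allows one week, not 24 hours |
| Laboratory outputs (SAP Section 4.5.3.1) | Grade 3 or higher ALT, hepatobiliary abnormalities, GSK3228836 liver events, PegIFN ALT guideline events | Seriousness, causality, outcome |

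SAP Section 4.5.2.1 takes seriousness, drug-relatedness, outcome and action taken from AESI records. Action taken can partly be recovered from the hold/stopping profiles and the PegIFN dose-modification summary in SAP Section 4.5.3.1. The other items need an AE entry.

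**The case against.** The best defence is that the exclusions are conditional. Severity is judged against the participant's own condition, and Section 5.1 admits people on stable NA therapy with HBV DNA below 90 IU/mL and ALT at most 2 x ULN. For them, ALT above 10 x ULN or an admission is readily worse than expected. The statements that flares are expected sit in a drug-risk table and are not recording rules. Section 8.3.7.1 itself calls the cause of flares uncertain. The IDMC and the internal safety team also review safety data at large (Sections 8.8 and 8.9).

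Most of this stands, and it rules out several stronger conclusions that a reader might draw:

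- *Flares are excluded outright.* They are not: the severity exception and the exacerbation bullet both allow recording.
- *Possible Hy's Law cases need not be reported.* Note 3 requires it. The fault there is an unreconciled contradiction.
- *Flares disappear from the trial.* The routes listed above keep them in the data.
- *A count per arm follows.* Section 2.3.1 gives PegIFN on-treatment flare rates above 10 x ULN of 12% (HBeAg-negative) and 18% (HBeAg-positive). With 50 per arm, 0.12 x 50 = 6 and 0.18 x 50 = 9. This assumes that everyone receives PegIFN and that the rates carry over to NA-suppressed participants treated for at most 24 weeks. The documents establish neither, and the upper figure also needs every participant to be HBeAg-positive. Nor do they say what share would go unrecorded.

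The defence does not remove the dependence on judgement. A document that tells investigators to expect flares weakens an exception that turns on what was expected.

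**Conclusion.** The concern holds as a conflict in current text. Sections 10.3.1 and 10.3.2 are not reconciled with Section 8.3.7.1, Table 17 note 3 or SAP Section 4.5.2.1. Whether a hepatitis flare becomes an AE, an AESI or an SAE can therefore vary between investigators who all follow the protocol. The possible loss is in classification and prompt reporting: seriousness, causality, outcome and the 24-hour SAE route. ALT values are not lost, and the primary efficacy endpoint is untouched. The number of events affected cannot be derived from the documents, and the conclusion does not depend on one.

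A reader might infer that a hospitalised or fatal flare could lawfully go unreported. The documents do not support that: Section 8.3.4 commits the sponsor to country-specific safety-reporting requirements, and every death has its own form. What can be said is that leaving a hospitalised flare out of SAE reporting would be consistent with Section 10.3.2 as written.

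**What to change.** In protocol Sections 10.3.1 and 10.3.2, add a study-specific statement along these lines: *ALT increases that meet a liver threshold already set in Table 9 or Section 7.2.2, hepatitis flare and hepatic decompensation are recorded as AEs whether or not they are attributed to hepatitis B. They are SAEs when a seriousness criterion is met. Table 17 note 3 applies notwithstanding the rule that a non-AE cannot be an SAE.* Qualify the examples in Section 10.3.2 on admission and death from the studied disease to match, and align Section 8.2.5.

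In SAP Section 4.5.2.1, show the laboratory-defined ALT results already planned in Section 4.5.3.1 beside the coded ALT AESI. The amendment summary says enrolment was already complete, so some flares may have been classified under the present wording. The paired display would make any gap between laboratory flares and AE records visible.

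The cost is a protocol clarification, a change in table layout and somewhat more AE and SAE reporting. No dose, threshold or management rule changes.

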10.3.3. Definition of Cardiovascular Events

Cardiovascular Events (CV) Definition:
Investigators will be required to fill out the specific CV event page of the CRF for the following AEs and SAEs:

- Myocardial infarction/unstable angina
- Congestive heart failure
- Arrhythmias
- Valvulopathy
- Pulmonary hypertension
- Cerebrovascular events/stroke and transient ischemic attack
- Peripheral arterial thromboembolism
- Deep venous thrombosis/pulmonary embolism
- Revascularisation

10.3.4. Recording and Follow-Up of AE and SAE

AE and SAE Recording

 • When an AE/SAE occurs, it is the responsibility of the investigator to review all documentation (e.g., hospital progress notes, laboratory, and diagnostics reports) related to the event. • The investigator will then record all relevant AE/SAE information. • It is not acceptable for the investigator to send photocopies of the participant's medical records to GSK in lieu of completion of the GSK required form. • There may be instances when copies of medical records for certain cases are requested by GSK. In this case, all participant identifiers, with the exception of the participant number, will be redacted on the copies of the medical records before submission to GSK. • The investigator will attempt to establish a diagnosis of the event based on signs, symptoms, and/or other clinical information. Whenever possible, the diagnosis (not the individual signs/symptoms) will be documented as the AE/SAE.
Assessment of Intensity

The investigator will make an assessment of intensity for each AE and SAE reported during the study and assign it to 1 of the following categories:
 
 • Mild: An event that is easily tolerated by the participant, causing minimal discomfort and not interfering with everyday activities. • Moderate: An event that causes sufficient discomfort and interferes with normal everyday activities. • Severe: An event that prevents normal everyday activities. An AE that is assessed as severe should not be confused with an SAE. Severe is a category utilised for rating the intensity of an event; and both AE and SAE can be assessed as severe.

- An event is defined as ‘serious’ when it meets at least 1 of the predefined outcomes as described in the definition of an SAE, NOT when it is rated as severe.

Assessment of Causality

The investigator is obligated to assess the relationship between study intervention and each occurrence of each AE/SAE.

- A "reasonable possibility" of a relationship conveys that there are facts, evidence, and/or arguments to suggest a causal relationship, rather than a relationship cannot be ruled out.
- The investigator will use clinical judgment to determine the relationship.
- Alternative causes, such as underlying disease(s), concomitant therapy, and other risk factors, as well as the temporal relationship of the event to study intervention administration will be considered and investigated.
- The investigator will also consult the Investigator’s Brochure (IB) and/or Product Information, for marketed products, in his/her assessment.
- For each AE/SAE, the investigator **must** document in the medical notes that he/she has reviewed the AE/SAE and has provided an assessment of causality.
- There may be situations in which an SAE has occurred and the investigator has minimal information to include in the initial report to GSK. However, **it is very important that the investigator always make an assessment of causality for every event before the initial transmission of the SAE data to GSK.**
- The investigator may change his/her opinion of causality in light of follow-up information and send an SAE follow-up report with the updated causality assessment.
- The causality assessment is one of the criteria used when determining regulatory reporting requirements.

Follow-up of AE and SAE

- The investigator is obligated to perform or arrange for the conduct of supplemental measurements and/or evaluations as medically indicated or as requested by GSK to elucidate the nature and/or causality of the AE or SAE as fully as possible. This may include additional laboratory tests or investigations, histopathological examinations, or consultation with other health care professionals.
- If a participant dies during participation in the study or during a recognised follow-up period, the investigator will provide GSK with a copy of any post-mortem findings including histopathology.
- New or updated information will be recorded in the originally submitted documents.

- The investigator will submit any updated SAE data to GSK within 24 hours of receipt of the information.

The DAIDS Table [DAIDS, 2017] is used for grading AEs and provided as a guidance for patient management for the consideration of the PI. The DAIDS table will be used to grade the severity of an AE that is not specifically identified in the grading table. In addition, all deaths related to an AE are to be classified as grade 5.

The DAIDS Table is available at the following link:

<https://rsc.niaid.nih.gov/clinical-research-sites/grading-severity-adult-pediatric-adverse-events-corrected-version-two-one>

